Further understanding of the role of ACTH in kidney disease is provided by a recent study by Bombback in patients with refractory nephrotic syndrome despite appropriate immunosuppression. ACTH was effective in inducing remission. Twenty-one patients with nephrotic syndrome were treated with ACTH 80 mg SQ twice a week: 11 with idiopathic membranous nephropathy, 4 with membranoproliferative glomerulonephritis, 1 with focal segmental glomerulosclerosis, 1 with minimal change disease, 1 with immunoglobulin A (IgA) nephropathy, 1 with Class V systemic lupus erythematosus (SLE) glomerulonephritis, 1 with monoclonal diffuse proliferative glomerulonephritis, and 1 with unbiopsied nephrotic syndrome. Eleven out of 21 patients (52%) achieved a complete or partial remission, with 4 (19%) in complete remission. Five patients reported steroid-like adverse effects (2 weight gain, 2 hyperglycemia, 1 bone demineralization), but there were no severe infections [30].

The mechanism of action of Acthar in the treatment of SLE is currently being investigated. H.P. Acthar Gel and endogenous ACTH stimulate the adrenal cortex to secrete cortisol, corticosterone, aldosterone, and a number of weakly androgenic substances by binding to MC2R. The trophic effects of endogenous ACTH on the adrenal cortex are not well understood beyond the fact that they appear to be mediated by cAMP. Prolonged administration of large doses of Acthar induces hyperplasia and hypertrophy of the adrenal cortex. The release of endogenous ACTH is under the influence of the nervous system via the regulatory hormone released from the hypothalamus and by a negative corticosteroid feedback mechanism. Elevated plasma cortisol suppresses pituitary ACTH release. Acthar binding to melanocortin receptors in a variety of cell types, including immune cells, is likely responsible for some of the beneficial effects.

Recent data from Multiple Sclerosis (MS) suggests the ACTHar gel (80 IU X3 daily doses) is superior to 1000 mg of IV Medrol given monthly for 12 months in the treatment of MS exacerbations [31], raising the possibility of improved outcomes in LN with ACTHar in a manner similar to that described by Gourley: the addition of Medrol to the standard of care for LN improved outcomes [8].

Urinary Biomarkers

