Dose finding study of patients with a recent flare of LN, and biopsy proven LN (Class III, IV) treated with CellCept 3 grams daily and ACTHar gel 80 U biw or Acthar gel 80 U qod. The dose of 80 U biw was chosen based on the published literature in MN. However, in an attempt to improve outcomes we also suggest a higher dose of 80 U qod to be used for one month of "induction". Patients in the 80 U qod arm will be tapered to 80 biw after the first month of therapy. In all groups, patients can be on a prednisone dose of ≤ 20 mg prior to initiating therapy with CellCept or ACTHar. Based on the investigator's judgment, patients will be switched to oral prednisone for worsening lupus nephritis or extra-renal lupus. Patients will be maintained on ACTHar for a total of 3 months. Patients with partial response will be offered the option to continue ACTHar 80 U biw for a total of 6 months. Each dosing arm will include 10 patients.

Biomarkers

Patients whose renal biopsies are available (we expect that 80% of patients will have a biopsy done within 1 month of the screening visit) will have frozen sections stained for MCR using anti-MCR antibodies in the manner described by Gong [35]. Similarly, skin biopsy samples obtained at D 0 and week 24 will be stained for MCR. The readout of MCR activation by ACTH in the skin will be ICAM-1, VCAM1, mEPCR. Also, levels of ICAM-1, VCAM-1, and E-selectin will be evaluated in urine samples collected at D 0, weeks 4, 12 and 24. Our center has extensive expertise in the measurement of these cytokines. Our collaborator [name] will supervise the work of examining all biomarkers. We hypothesize that dermal and urinary biomarkers are likely to decrease faster in response to treatment with ACTHar as a consequence of the direct activation of the MCR.

Treatment Overview

Screening protocol –as per attached schedule of assessments

CONCOMITANT MEDICATIONS

Participants may receive all required and non-prohibited concomitant medications as clinically indicated. Prednisone in a dose of ≤ 20 mg daily is allowed at study entry, but should be tapered to below 10 mg daily as tolerated by week 24.

Prophylactic Medications

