The investigator will maintain adequate records of the disposition of the investigational agent, including the date and quantity of drug that was received, the participants to whom the drug was dispensed (participant by participant accounting), and an account of any drug accidentally or deliberately destroyed. Records for receipt, storage, use, and disposition of the study drug will be maintained on site. A drug-dispensing log will be kept current for each participant and will contain the identification of each participant and the date and quantity of drug dispensed. All records regarding disposition of the investigational product will be available for inspection by Questcor.

ASSESSMENT OF COMPLIANCE WITH STUDY MEDICATION

ACTH and MMF compliance will be checked at each visit.

Dosage and Administration of Acthar *Daily /weekly dose, administration, frequency*

Patients will be treated with CellCept 3 grams daily and randomly assigned to ACTHar gel 80 U biw or Acthar gel 80 U qod.

The dose of 80 U biw was chosen based on the published literature in MN [30].

In an attempt to improve outcomes, we also suggest a higher dose of 80 U qod to be used for one month of “induction”. Patients in the 80 U qod will be tapered to 80 biw after the first month of therapy.

Patients will be maintained on ACTHar for a total of 3 months.

Patients that do not achieve complete response at week 12 will be offered the option to continue ACTHar 80 U biw for a total of 6 months, or 24 weeks.

Laboratory Testing and Study Schedule --see schedule of events

Patient Monitoring and Evaluation *Contingencies for patients not responding (i.e. dose adjustment, schedule change)*

Glucocorticoids may be increased during the study for worsening renal and extra-renal manifestations of SLE. The dose may be increased as required by the clinical manifestations up to 1 mg/kg/d. ACTHar will be discontinued and patients will be considered non-responders. Renal relapses, as defined by increase in proteinuria at two consecutive visits will require discontinuation of the study regimen and treatment based on investigator preference.

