The major short-term side-effects of ACTH are salt and water retention, hypertension, hyperglycemia, central nervous system stimulation, peptic ulceration and immunosuppression. While such effects are reversible, if the use is prolonged, additional adverse effects including osteoporosis, cataracts, skin fragility, myopathy, Cushingoid facies, hirsutism, alopecia, fat re-distribution, and striae may occur, as well as infections which can be life-threatening.

Potential Pitfalls and Contingencies *Describe plans to address possible problems*

Study Drug Discontinuation

1. SLE Extra-renal Flare—severe BILAG A or SLEDAI flares
2. Renal Flare – increase proteinuria by 30% and/or increased in creatinine by 25% over the baseline visit 0, confirmed by repeat analysis. Proteinuria needs to be confirmed by a 24 hour urine P/C ratio.
3. ACTHar related steroid-like side effects – HTN, DM, hypoK refractory to optimal management
4. Severe life-threatening infections

Study drug can be decreased for ACTHar related AE, as described above. Patients will be closely monitored to document maintained efficacy. We propose the following taper regimen, 80 mg qod, decreased to 80 mg biw for one week if AE continues, decrease to 60 biw for one week, then 40 biw, and finally 20 biw.

If the study drug is discontinued for SLE related increased activity, the patients will be treated with the appropriate dose of prednisone and continued to be followed up until resolution of the symptoms. At the end of the 3 month treatment period, ACTH will be discontinued. In the event of adrenal insufficiency upon discontinuing the drug either for side effects or end of therapy, the previous dose of ACTH will be restarted and the above taper regimen will be followed.

Data Processing and Analysis

Statistical /Analytical Plan *Include data management and quality assurance*

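### The ACTHar reduction schedule is in mg or carries no unit while assigned doses are in U, and three sections differ on who may continue past 3 months

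*Combined protocol and SAP*

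**What the plan says.** **Units.** The Treatment Description has patients "treated with CellCept 3 grams daily and ACTHar gel 80 U biw or Acthar gel 80 U qod". Dosage and Administration of Acthar repeats this: patients are "randomly assigned to ACTHar gel 80 U biw or Acthar gel 80 U qod". It then adds a planned step-down in the higher-dose arm: "Patients in the 80 U qod will be tapered to 80 biw after the first month of therapy".

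Study Drug Discontinuation, under Potential Pitfalls and Contingencies, sets the reduction schedule: "We propose the following taper regimen, 80 mg qod, decreased to 80 mg biw for one week if AE continues", and then "decrease to 60 biw for one week, then 40 biw, and finally 20 biw". The same section uses this schedule twice: for ACTHar-related adverse events, and after ACTHar is restarted for adrenal insufficiency, whether the drug was stopped for side effects or at the end of therapy.

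The background (Rationale for ACTH) describes the nephrotic syndrome study, cited in the text as [30], in mg: "Twenty-one patients with nephrotic syndrome were treated with ACTH 80 mg SQ twice a week". The dosage section cites [30] as the basis for 80 U biw.

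**Duration.** The Treatment Description and the dosage section both set 3 months of ACTHar as the default and add an optional extension at 80 U biw to 6 months (24 weeks). The Treatment Description offers the extension to partial responders. The dosage section says: "Patients that do not achieve complete response at week 12 will be offered the option to continue ACTHar 80 U biw". Study Drug Discontinuation says: "At the end of the 3 month treatment period, ACTH will be discontinued", and does not mention an extension. The primary outcome is complete response at 6 months.

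**The concern.** A reduction schedule is followed when a patient is already having a problem with the drug or with its withdrawal. Here the reader has to infer the unit on every step, because two steps use a different unit from the assigned dose and three have none. The background cannot serve as a key, because it uses mg for the study that the dosage section cites in support of a dose in U.

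The duration text matters for a different reason. The primary endpoint falls at the latest date to which the extension can run. Whether a given patient is on ACTHar at that assessment, or has been off it for about 3 months, depends on which section the site follows. If patients of the same response status are handled differently, the 6-month response rate in each arm does not correspond to one defined regimen.

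**Working it through.** The documents state no cumulative dose and no conversion, so there is no figure of theirs to reproduce. The check sets the sections side by side.

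**1. Units, step by step**

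| Step | Assigned-dose sections | Reduction schedule |
|---|---|---|
| 80 qod | U | mg |
| 80 biw | U; unit omitted where the step-down is described | mg |
| 60 biw | not used | no unit |
| 40 biw | not used | no unit |
| 20 biw | not used | no unit |

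The first two rows agree in number and frequency; only the label differs. The last three rows have no counterpart elsewhere to check against. After month 1 both arms are on 80 biw unless the dose was reduced earlier. A patient who restarts for adrenal insufficiency at the end of therapy would therefore normally enter at the second row and descend through the three unlabelled steps.

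The background uses mg for the nephrotic syndrome study and IU for the multiple sclerosis study. The link between the mg description and the 80 U dose rests on the shared in-text number [30]. The numbering of the reference list is offset from the text: entry 30 is a kidney-transplant paper, and the ACTH gel trial is entry 32.

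**2. Who may continue past 3 months**

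The Treatment Description gives no week for judging partial response; week 12 is assumed here.

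| Status at week 12 | Treatment Description | Dosage section | Study Drug Discontinuation, read literally |
|---|---|---|---|
| Complete response | stops | stops | stops |
| Partial response | may extend | may extend | stops |
| No response | stops | may extend | stops |

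Only the first row is consistent. The third is the firmer conflict, because the two sections that create the extension disagree with each other.

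**3. How many patients the third row could cover**

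Patients per arm = 10 × (1 − total response at week 12). The documents give no week-12 rate. Their expected rates, set against the 6-month outcome, are 20% complete and 50% total. Taking 50% as an assumption for week 12 gives 10 × 0.50 = 5 per arm. At 30% it is 7, and at 70% it is 3. These are upper limits on those who would actually continue: the extension is optional, and some non-responders will already have stopped under the flare rules. Each patient is 1/10, or 10 percentage points, of an arm's response rate.

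**4. What extending means for dose (full adherence)**

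- Biw arm: 2 × 80 = 160 U/week. At 12 weeks, 160 × 12 = 1,920 U. At 24 weeks, 160 × 24 = 3,840 U.
- Qod arm, 28-day month: 14 × 80 = 1,120 U in month 1. At 12 weeks, 1,120 + 8 × 160 = 2,400 U. At 24 weeks, 1,120 + 20 × 160 = 4,320 U, a ratio of 1.8.

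These figures compare an extended with a non-extended patient. That gap exists by design under either dosing section, so it does not measure the inconsistency.

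**The case against.** **The unit is a slip that nobody would act on.** The first two steps reproduce the assigned regimens exactly apart from the label. The dosing text itself drops the unit in describing the step-down, and omitting it from the later terms of a list is ordinary shorthand. The background and the dosage section describe the same twice-weekly 80 under one citation number, once in each unit. Most of this stands. A reader might infer that the schedule introduces a second, mg-based dose scale, or that its numerical steps conflict with the assigned doses. The documents support neither. What remains is that the reader must infer the unit, in the one place where the plan instructs how to reduce the drug.

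**The 3-month stop is the default everywhere.** Both dosing sections also say 3 months, so the discontinuation sentence can be read as restating that default without repeating the exception. This stands too. A reader might infer that the section ends ACTHar for every patient and flatly contradicts a 24-week regimen. The text does not say that: 24 weeks is optional and tied to response, and the stop conflicts with it only by leaving the exception out. The disagreement over eligibility between the Treatment Description and the dosage section is not met by this argument.

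**Dispensing is already logged.** Drug accountability records the date and quantity dispensed per participant, and compliance is checked at each visit. That helps, but quantity dispensed is not dose given, and a log cannot settle which unit a reduction step was meant to carry.

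**Conclusion.** The concern holds on two limited points.

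- **Unit label.** All five steps of the reduction schedule lack a unit that agrees with the assigned doses: two are in mg and three have none, with no conversion in the documents. It is probably one labelling error, since the numbers and frequencies match where they can be compared. It still warrants correction because the instruction is operative and bears on patient safety.
- **Extension.** The plan does not state consistently who may be on ACTHar at the 6-month primary endpoint. A patient without response at week 12 may extend under the dosage section, may not under the Treatment Description, and stops under the discontinuation text. The illustration of about 5 patients per arm (3 to 7 for total response between 70% and 30%) assumes a week-12 rate that the documents do not give, and is an upper limit.

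A reader might take the roughly twofold difference in cumulative dose as the size of the defect. It is simply 12 against 24 weeks, and it would remain after the wording was harmonised if the extension were kept. No view is taken on which unit, dose or stopping rule is correct.

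**What to change.** Reconcile Rationale for ACTH, Treatment Description, Dosage and Administration of Acthar, and Study Drug Discontinuation so that:

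1. every ACTHar dose, including each of the five reduction steps and the description of the cited study, is in one unit, or the relation between units is stated;
2. eligibility for the extension is stated once, with the week at which response is judged, and cross-referenced elsewhere;
3. the discontinuation section says whether its 3-month stop excepts patients who take up the extension.

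The clinical team must decide which text stands. Record the dose actually given in the chosen unit, with its dates, so that each patient's ACTHar status at the 6-month assessment is known. This is a recording requirement only; the Statistical/Analytical Plan contains no exposure analysis and none is needed for this point.

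The cost is a wording amendment and a check that the dispensing log uses the same unit. Sample size and analysis are unaffected.

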Recurrent renal flares cause renal damage leading to glomerulosclerosis and irreversible deterioration of renal function [9]. Safe and effective maintenance therapies are needed to prevent renal relapses, reduce progression to ESRD, and reduce the chance of adverse events. Clinical trials focusing on maintenance therapies by Contreras *et al.* [13], ALMS (Aspreva Lupus Management Study) [26] and Houssiau *et al.* (MAINTAIN) [27] suggest that MMF is at least equivalent to AZA for maintenance therapy. A summary of the maintenance trials is presented in **Table 3**. The current study patients will be maintained on MMF for total treatment duration of 2 years.

Non-immunomodulatory treatments are also used in the treatment of LN patients. These include ACE inhibitors, ARBs, and statins and are not restricted in this study.

C. RESEARCH DESIGN AND METHODS

Study Design

The study is a randomized, controlled phase IV, single center trial of ACTHar plus CellCept (Mycophenolate Mofetil), as defined by the ASPREVA Nephritis Trial (MMF 3000 mg daily) in the treatment of lupus nephritis. The primary outcome will be assessed at 6 months. Thereafter, subsequent therapy will be with CellCept maintenance 2000 mg daily.

Study Duration

Follow-ups for each patient will be conducted for a total of 24 months.

Primary Outcome

The proportion of participants who achieve a complete response at 6 months.

1. Complete response (CR) is defined as *all* of the following criteria having been achieved:
 - a. Stabilization of estimated glomerular filtration rate (i.e., a 6-month eGFR level \pm 10% of baseline) or improvement if the screening value is changed from patient's baseline
 - b. Inactive urinary sediment (red blood cells per high-power field [RBCs/HPF] <5-10, not due to gyn bleeding)
 - c. Urine protein/creatinine ratio <0.5

Secondary Outcomes

1. Frequency of responders = CR + Partial Responders (PR). PR = improvement from baseline of at least \geq 50% in all abnormal renal parameters (proteinuria and serum creatinine) without deterioration of any measurements at 6 months
2. Frequency of extra-renal flares as defined by the SELENA-SLEDAI Flare Index. Extra-renal disease activity measured by SELENA-SLEDAI and BILAG
3. Steroid -like side effects: increased in BP by 20 mmHg for both SBP and DBP, increased blood sugar with a fasting plasma glucose level \geq 126 mg/dl, weight gain \geq 10% of the initial weight, infections
4. Side effects

Inclusion Criteria

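### One restart rule for adrenal insufficiency can return a patient stopped for uncontrolled hypertension, diabetes or low potassium to the ACTHar dose that was stopped

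*Combined protocol and SAP*

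**What the plan says.** Three parts of the Study Drug Discontinuation text (under Potential Pitfalls and Contingencies) bear on this.

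- **Reasons to stop.** Item 3 of the list covers steroid-like side effects of ACTHar: "HTN, DM, hypoK refractory to optimal management". Item 4 is "Severe life-threatening infections". Items 1 and 2 are extra-renal and renal flares.
- **Dose reduction.** "Study drug can be decreased for ACTHar related AE, as described above". The reduction ladder starts at 80 every other day, "decreased to 80 mg biw for one week if AE continues, decrease to 60 biw for one week", and then goes to 40 and finally 20 twice weekly.
- **Adrenal insufficiency.** If it occurs once the drug has been stopped, "either for side effects or end of therapy, the previous dose of ACTH will be restarted and the above taper regimen will be followed".

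Stops for lupus activity are dealt with separately in the same text, with prednisone. Stops for side effects and planned end of therapy share the single restart instruction.

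**The concern.** Item 3 applies only once optimal management has failed. Restarting the same dose restores the exposure that could not be managed. The protocol itself supplies the mechanism: Rationale for ACTH describes Acthar driving cortisol and aldosterone secretion, and Patient Monitoring and Evaluation names fluid retention, hypertension and hyperglycemia among the main short-term effects of ACTH.

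The two situations that the rule joins are different. At planned end of therapy the patient has tolerated the dose, so going back to it and tapering is sensible. After an item 3 stop the dose is the suspected cause of the problem. An investigator who follows the protocol as written would have to re-expose that patient, and one who judges this unsafe would have to deviate from it.

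**Working it through.** The plan gives no figure to reproduce. The check consists of reading the rules against each other and converting the doses.

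**1. Does the rule reach an item 3 stop?** Yes. Item 3 itself describes these events as side effects, and the restart sentence names side effects as one of its two triggers. The restart is mandatory, whereas dose reduction is optional. Treatment Description, Dosage and Administration of Acthar, and Patient Monitoring and Evaluation contain no exception, lower restart dose or alternative for these patients.

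**2. What must happen before the rule applies?** Three events in sequence: a side effect refractory to management, a stop because of it, and then adrenal insufficiency. A stop under item 3 alone does not trigger a restart.

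**3. What is the restart dose?** Assumptions: the ladder's mg means U, as in the dosing sections; every-other-day dosing is 3.5 doses per week; twice weekly is 2; and the previous dose, which is not defined, is the dose in use when the drug was stopped.

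| Dose when stopped | Calculation | U/week on restart |
|---|---|---|
| 80 every other day | 80 × 3.5 | 280 |
| 80 twice weekly | 80 × 2 | 160 |
| 60 twice weekly | 60 × 2 | 120 |
| 40 twice weekly | 40 × 2 | 80 |
| 20 twice weekly | 20 × 2 | 40 |

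The first row can arise only in the higher-dose arm during its first month. The last three arise only if the dose was reduced before the stop.

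**4. How long is re-exposure?** It cannot be computed. The ladder gives one week at 80 twice weekly, but as a step down from every-other-day dosing, and one week at 60 twice weekly. It gives no time at 80 every other day, at 40 or at 20. For a patient restarted at 80 twice weekly, it is unclear whether the stated week applies or the next step is 60.

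**5. How often would it happen?** The documents give no rate for refractory events, for stops under item 3 or for adrenal insufficiency after stopping. With 10 patients per arm there are 10 + 10 = 20 in all, so only a small number could be affected.

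**6. Does the rule reach item 4?** Only if a life-threatening infection counts as a side effect. The restart sentence does not say. Two places point that way: Secondary Outcomes, item 3, ends its list of steroid-like side effects with "10% of the initial weight, infections", and Patient Monitoring and Evaluation includes immunosuppression and life-threatening infection among the adverse effects of ACTH.

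**The case against.** The strongest case on the other side is that this is a narrow, conditional event. The ladder sits just before the restart rule, so a patient may have been stepped down before stopping and would then restart at as little as 40 U/week. A taper follows in any case. Tapering ACTH also has a rationale, since the protocol describes cortisol feedback suppressing pituitary ACTH. All of this stands, and it limits the size of the point. It does not remove it: the ladder is optional, and nothing prevents a restart at 160 or 280 U/week.

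Several stronger readings are tempting, but the documents do not support them.

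- *Every patient stopped for hypertension, diabetes or low potassium goes back to the full assigned dose.* Adrenal insufficiency must follow, and the previous dose may already be a reduced one.
- *Re-exposure lasts at least two weeks at 120 U/week or more.* This adds one week at 160 to one week at 120, but the ladder does not clearly assign the first of those weeks to someone restarted at 80 twice weekly.
- *About 2 of the 20 patients would be affected.* The cited series of 21 ACTH-treated patients reports "2 weight gain, 2 hyperglycemia, 1 bone demineralization), but there were no severe infections". Two of 21 is 9.5%, and 20 × 2/21 = 1.9. But the protocol does not say that those events were refractory or led to stopping, its account mentions no adrenal insufficiency, and the series used only the twice-weekly dose.
- *Replacement glucocorticoid is forbidden.* Prohibited Medications limits immunosuppressive agents to baseline prednisone and anti-malarials unless the protocol prescribes others, but the drugs it names as prohibited are Cytoxin preparations, methotrexate and cyclosporine. Concomitant Medications states: "Participants may receive all required and non-prohibited concomitant medications as clinically indicated". Replacement for adrenal insufficiency fits that permission.

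**Conclusion.** The point holds in a limited form. The protocol states one mandatory restart rule for two situations that need different handling. In a patient stopped under item 3 who then develops adrenal insufficiency, it restores for a time the dose at which the side effect could not be controlled: 280 U/week, 160 U/week, or less after prior reduction. These figures rest on reading the previous dose as the dose in use at the stop and the ladder's mg as U. Frequency and duration are unknown. Coverage of item 4 depends on whether infection is treated as a side effect.

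A reader might infer that the primary endpoint is affected. It is not: under Patient Monitoring and Evaluation, non-responder status attaches to glucocorticoid increases for worsening lupus, which replacement for adrenal insufficiency is not. The point is worth considering for patient safety and calls for no change to the analysis.

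**What to change.** Split the adrenal-insufficiency sentence by reason for stopping.

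- **End of therapy:** keep the present rule.
- **Stop under item 3, and under item 4 if infection is treated as a side effect:** do not restart ACTHar at the dose that was stopped. Treat adrenal insufficiency with replacement-dose glucocorticoid, tapered as tolerated. If ACTHar must be resumed, use a ladder step below the stopped dose, for example 80 twice weekly (160 U/week) after 80 every other day, or 60 twice weekly (120 U/week) after 80 twice weekly. A patient stopped at 20 twice weekly has no lower step, so only replacement applies.

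The choice between replacement and a lower step is clinical, and the documents do not settle it, so both can be left open to the investigator. The cost is two or three sentences in place of one, with no added visits, tests or patients. The downside is short-term replacement glucocorticoid in a few patients, with steroid effects of its own; the protocol's background lists diabetes, raised blood pressure and infection risk.
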